Neuropathic pain was defined in 2011 by the International Association for the Study of Pain (IASP) as the direct consequence of a lesion or disease affecting the somatosensory system (5). Nociceptive pain corresponds to a normal—although variably adapted—response of the physiological "alarm system" triggered by a lesion threatening tissue integrity. In contrast, "neuropathic pain is always pathological, as it reflects disturbances and dysfunctions of physiological nociceptive systems" (6). Pain is described as mixed when it includes both neuropathic pain and pain related to nociceptive overload, which is often the case in tumor progression (5).

Etiology of Neuropathic Pain in Patients With Breast Cancer

Breast cancer treatments are divided into locoregional treatments—surgery and radiotherapy—and systemic treatments such as chemotherapy (including targeted therapies) and hormone therapy administered either as adjuvant or neoadjuvant therapy.

Among these treatments, only hormone therapy does not directly induce neuropathic pain, although prolonged administration may lead to nociceptive pain of musculoskeletal origin (7). Chemotherapy can also cause neuropathic pain as part of a sensorimotor peripheral neuropathy, which most often improves after discontinuation of treatment (5). Adjuvant radiotherapy may complement surgery. Irradiation may target the breast, the chest wall in cases of total mastectomy, and possibly regional lymph nodes. The risk of radiation-induced plexopathy exists, although it is less frequent with current radiotherapy techniques (8).

Surgery is often the first treatment for breast cancer. It may be breast-conserving, through partial mastectomy (lumpectomy or quadrantectomy), or non-conserving, through total mastectomy. These procedures are frequently combined with axillary surgery: either axillary lymph node dissection involving removal of 8–10 lymph nodes, or sentinel lymph node biopsy, which consists of identifying and excising the first lymph node(s) draining the breast. Axillary dissection is performed only if the sentinel lymph node is metastatic (9).

Intercostobrachial Neuralgia (ICBN)

Intercostobrachial neuralgia (ICBN), also referred to as Intercostobrachial Neuralgia (10) or Post-Mastectomy Pain Syndrome (PMPS), was first described by Wood in 1978 as “a chronic pain that begins immediately or soon after a mastectomy or lumpectomy and affects the anterior chest, axilla, and/or upper half of the arm.”

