These postsurgical pains are related to injury of nerves within the breast region. In particular, the intercostobrachial nerve may be transected, stretched, or compressed during surgery. However, literature reports indicate that nerve injury does not always result in pain.

Furthermore, axillary dissection may lead to upper-limb lymphedema, which can maintain or exacerbate pre-existing intercostobrachial neuralgia. Breast-conserving surgery appears to be associated with a lower risk of ICBN than mastectomy combined with axillary dissection. Postoperative complications, such as hematoma or infection, also seem to increase the incidence of ICBN. Overall prevalence ranges between 32% and 58%, though it varies widely across studies and depends on the pain assessment method used (8).

[figure not shown]

Figure 1: Innervation of the breast and location of nerves at risk during surgery (Reg Anesth Pain Med, 2014, Wijayasinghe N. et al.)

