The prevalence of chronic pain after breast cancer is estimated at 47% in a study by Gartner involving 3,254 patients in Denmark in 2009 (19). Other studies have assessed the incidence of chronic neuropathic pain after breast surgery, but most lack sufficient power for generalization to all breast cancer patients.

Risk Factors for Chronic Neuropathic Pain After Breast Cancer Surgery

Several risk factors for chronicization have been identified in the literature. Among them, younger age—≤49 years in Mejdahl's Danish study (12) and 18–39 years in Gartner's study (19)—is associated with higher risk. Breast cancer in younger patients is often more aggressive, warranting more intensive treatments (19, 20). Conversely, age >70 years appears protective and is associated with fewer chronic postsurgical pain symptoms (21).

Axillary lymph node dissection is the second unanimously recognized risk factor, due to the risk of intercostobrachial nerve injury. According to Gartner, the risk of developing neuropathic pain is higher after axillary dissection than after sentinel lymph node biopsy (19). Additional risk factors include adjuvant chemotherapy, adjuvant radiotherapy, and preexisting chronic pain conditions such as chronic low back pain, osteoarthritis, or fibromyalgia (19, 20).

The presence of early neuropathic pain symptoms is also a predictor of chronic neuropathic pain (22). Finally, depression, psychological vulnerability, and stress are the psychological factors most strongly associated with chronic postsurgical pain (23).

Consequences of Pain Chronicization

Moderate-to-severe neuropathic pain correlates strongly with reduced quality of life (24). Although no specific studies have evaluated the economic impact of chronic pain after breast surgery, reduced quality of life is a key driver of the overall financial burden of breast cancer (25, 26).

Importance of Early and Appropriate Management

Early diagnosis, assessment, and management of neuropathic pain are essential to prevent chronicization, improve the quality of life of breast cancer surgery patients, and facilitate faster return to work. Early neuropathic pain management may also reduce societal costs, particularly for national health insurance systems.

References

1. HAS. Synthèse d'avis de la commission de transparence – QUTENZA (capsaïcine, antalgique local en patch. http://www.has-santefr/portail/upload/docs/application/pdf/2011-04/synthese_davis_qutenza_-_ct-8291pdf 2011.

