To evaluate the impact of pain duration prior to treatment initiation on therapeutic response.	Treatment effect will be assessed at 2 and 6 months using the 11-point NRS in both arms. Pain duration prior to initiation of treatment is self-reported, expressed in months, and collected at baseline	6 months
INCLUSION CRITERIA	
 1) Male or female patient who has undergone first-line surgical treatment for breast cancer, regardless of the type of surgery. 2) Age ≥ 18 years. 3) Healthy and non-irritated skin over the painful areas to be treated. 4) Neuropathic pain of the breast and/or axillary region consistent with intercostobrachial neuralgia, with a DN4 score ≥ 4, diagnosed between 3 and 12 months after surgery. 5) Written informed consent obtained and signed by the patient. 6) Adult patient covered by a national health insurance scheme. 	
NON-INCLUSION CRITERIA	
 1) Specific contraindications to the study treatments: 
 a. Pregabalin: hypersensitivity to the active substance or any excipient. b. Capsaicin: hypersensitivity to the active substance or any excipient. 2) Patient with diabetes. 3) Prior treatment with capsaicin or pregabalin between surgery and study inclusion. 4) Ongoing opioid treatment > 80 mg/day of morphine or equivalent at the time of inclusion. 5) Topical pain treatment within 7 days prior to inclusion. 6) Uncontrolled hypertension (systolic blood pressure ≥ 180 mmHg or diastolic blood pressure ≥ 90 mmHg) or recent history of cardiovascular events (stroke, myocardial infarction, pulmonary embolism). 7) Patient with chronic kidney failure. 8) Pregnant or breastfeeding women, or women who may become pregnant. 	

- 9) Individuals deprived of liberty or under legal protection (including guardianship or curatorship).
10) Inability to comply with the study's medical follow-up.

E) INVESTIGATIONAL TREATMENT DESCRIPTION

Active Ingredient (INN)	Brand Name	Pharmaceutical Form	Route of Administration	Dose per Administration
Capsaicin	QUTENZA	Cutaneous patches	Topical	640 micrograms of capsaicin per cm ² Patch size: 280 cm ²
Pregabalin	LYRICA	Capsule	Oral	50 mg to 600 mg

Therapeutic schema

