DESCRIPTION OF ANALYSIS SETS	
Description of planned statistical methods
 
A descriptive analysis of the study sample will be performed. Data will be presented as follows:
 
 • Qualitative variables: expressed as percentages. • Quantitative variables: expressed as mean and standard deviation, or median and range, depending on the distribution. 
Comparisons will be performed as follows:
 
 • Qualitative variables: using the Chi-square test or Fisher's exact test when appropriate. 
Quantitative variables: using Student's t-test or a non-parametric test (Wilcoxon test) depending on distribution and normality assumptions.
 
Definition of Analysis Populations
 
 • The ITT population includes all randomized patients in the CAPTRANE study. Patients are analyzed according to the treatment arm to which they were randomized, regardless of the treatment actually received. • Modified Intention-to-Treat Population (mITT) • The mITT population includes all randomized patients who received at least one administration of study treatment; i.e., excluding patients withdrawn prematurely or incorrectly included before receiving treatment. Patients are analyzed according to their allocated arm, regardless of treatment actually received. • Per-Protocol Population (PP) • The PP population includes all randomized patients who received the allocated treatment according to the protocol. Patients who received any treatment other than that assigned are excluded from the analysis. • If non-inferiority is demonstrated at the pre-specified 0.4 threshold (primary endpoint in the PP population), a Student's t-test will be used to compare the mean 24-hour maximum NRS pain scores at T2 (2 months after randomization) between the capsaicin and pregabalin arms, in the mITT population. • Mean 24-hour NRS scores at T6 will be compared between arms using a Student's t-test. • The percentage of patients with at least a "notable improvement" (PGIC score ≥ 5) will be compared between arms using a Chi-square test. • Reduction in painful area will be expressed as a percentage relative to baseline. • Differences in painful area between T2–T0 and T6–T2 will be compared using a Student's t-test. • All grade ≥ 2 adverse events will be described by category and by treatment arm. • The number of patients experiencing at least one grade ≥ 2 toxicity event will be compared using a Chi-square test. • The percentage of patients with $\geq 5\%$ weight gain will be compared between arms using a Chi-square test. • A subgroup analysis of NRS pain scores at T2 and T6 will be performed among patients with probable anxiety disorder and those with probable depressive disorder according to baseline HADS scores. • A multivariable linear regression model will be used to estimate the impact of pain duration before inclusion (expressed in months) on pain intensity at T2 and T6 (NRS), adjusted for:

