------------------------------	---

	
 - baseline NRS pain score, - treatment arm. 
Statistical stopping rules
 
An interim analysis will be conducted after inclusion of 150 patients per arm based on the primary endpoint (NRS at T6).
 
If a statistically significant difference in efficacy is observed at $\alpha = 0.005$, the study will be stopped for efficacy, regardless of which treatment demonstrates superiority.
 
Handling of missing, unused, or invalid data
 
Missing data for the numerical pain scale (NRS), painful area, and PGIC will not be imputed.
 
The proportion of missing data will be compared between arms using a Chi-square test.
 
Baseline characteristics of patients with missing data will also be compared.
 
Missing data for quality-of-life questionnaires (QLQ-C30, QLQ-BR23, EQ-5D) may be imputed according to EORTC manual recommendations.
 
Management of amendments to the analysis plan
 
Modifications to the statistical analysis plan may be proposed by the data monitoring committee (interim analysis, statistical tests, adverse event review, secondary objectives) if justified by emerging literature.
 
Protocol deviations will be identified and quantified.
 
Randomisation
 
Patients with a positive DN4 score will be randomized directly through the eCRF to be allocated to one of the following treatment arms:
 
 - Arm A (experimental): CAPSAICIN (patch), application of capsaicin patches to the painful area for 1 hour, with applications repeated every 3 months. - Arm B (standard): PREGABALIN (oral), oral pregabalin with progressive dose escalation. 
Validation of the randomization will automatically generate a confirmation email specifying the treatment arm allocated to the patient.
 
Randomization will be performed using balanced block allocation, stratified according to the following factors:
 
 - Study center - Pain intensity on the numerical rating scale (≥ 5) - Age (≥ 65 years) - HADS score (Incomplete, ≤ 18, > 18) - Pain duration (< 3 months or ≥ 3 months)
--	---

G) STUDY CALENDAR

DURATION OF INCLUSION PERIOD	36 months
TREATMENT DURATION	6 months
POST TREATMENT FOLLOW UP	6 months
STUDY COMPLETION DURATION (INCLUDING FU PERIOD)	42 months

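### The pain-duration model adjusts only for baseline NRS and arm, so its estimate is open to confounding by factors the protocol lists and should be reported as an association (minor)

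*Combined protocol and SAP*

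**What the plan says.** The secondary objective in Section C is "To evaluate the impact of pain duration prior to treatment initiation on therapeutic response". The exposure is observed, not assigned: "Pain duration prior to initiation of treatment is self-reported, expressed in months, and collected at baseline".

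The analysis is in Section F, at the end of the list of planned methods: "A multivariable linear regression model will be used to estimate the impact of pain duration before inclusion (expressed in months) on pain intensity". The NRS is taken from both follow-up visits (T2, T6). The full adjustment set follows: "baseline NRS pain score, - treatment arm".

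Section B describes what is related to pain after breast surgery. On surgery type, under Intercostobrachial Neuralgia: "Breast-conserving surgery appears to be associated with a lower risk of ICBN than mastectomy combined with axillary dissection". The subsection on risk factors for chronic neuropathic pain names younger age (with age over 70 as protective), axillary dissection, and depression and stress. It also says: "Additional risk factors include adjuvant chemotherapy, adjuvant radiotherapy, and preexisting chronic pain conditions".

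Age (cut at 65), the HADS score and pain duration (below 3 months, or 3 months and more) are stratification factors for randomisation. Neither age nor HADS is a covariate in the duration model. HADS has only a separate subgroup analysis.

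**The concern.** Stratifying the randomisation on duration balances duration between capsaicin and pregabalin. It does not make patients with short and long duration alike in other respects. The duration coefficient is an observational contrast within a randomised trial, and the word impact invites a causal reading.

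If a listed factor is related both to how long the pain had lasted at entry and to the later NRS score, the planned model attributes part of that factor's effect to duration. Section B argues for early management, and this is the only planned analysis that relates pain duration to outcome. Both arms start treatment on entry, so the randomised comparison cannot answer the question instead. A positive slope could be read as evidence for treating earlier.

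**Working it through.** **The plan's own figures.** The documents give no figure for this regression. The sample size formula supplies only the scale of the data. With SD 2.0, margin 0.4, one-sided alpha 0.045 and power 80%, n per arm = 2 × 2.0² × (1.695 + 0.842)² / 0.4² = 321.8, so 322 per arm and 644 in total, as stated. With 20% of 772 not evaluable, 772 × 0.8 = 617.6, or about 618. Both totals are used below.

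**Document check.** A confounder needs two links.
- *Factor to later pain.* Section B supports this for chronic pain after breast surgery in general.
- *Factor to pain duration before inclusion.* No section states this for any listed factor.

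**Illustration 1: a generic omitted factor.** Every effect input is an assumption: a binary factor with 50% prevalence, duration SD 2.5 months within factor level, total NRS SD about 2.0, N = 644 and true duration effect zero. Let the factor raise later NRS by g points and go with d months longer duration. The slope the planned model shows is approximately

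g × 0.25d / (2.5² + 0.25d²).

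For g = 1 and d = 2 this is 0.5 / 7.25 = 0.069 per month. The simulation (2,000 runs per setting; durations limited to 0–12 months) gave:

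| g (points) | d (months) | formula, per month | simulated, per month | over 9 months | rejection, two-sided 5% test | rejection with factor added |
|---|---|---|---|---|---|---|
| 0.5 | 0 | 0 | 0.000 | 0.00 | 5% | 5% |
| 0.5 | 0.5 | 0.010 | 0.010 | 0.09 | 7% | 5% |
| 0.5 | 1 | 0.019 | 0.020 | 0.18 | 11% | 5% |
| 0.5 | 2 | 0.034 | 0.036 | 0.32 | 28% | 5% |
| 1.0 | 0 | 0 | 0.001 | 0.01 | 5% | 5% |
| 1.0 | 0.5 | 0.020 | 0.020 | 0.18 | 11% | 5% |
| 1.0 | 1 | 0.038 | 0.040 | 0.36 | 29% | 6% |
| 1.0 | 2 | 0.069 | 0.071 | 0.64 | 75% | 4% |

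With d = 0 the planned model is unbiased, however strong the factor. The sign was fixed by making the factor go with longer duration; the opposite assumption reverses it.

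**Illustration 2: how much the time of onset matters.** Suppose entry is uniform over 3 to 12 months after surgery (variance 9²/12 = 6.75). Suppose also that the share of patients with transient treatment-related pain falls from p1 to p2 across that window, and that this pain later resolves by r points. The spurious effect over 9 months is about r × (p1 − p2) × λ, where λ is the slope of time since surgery on pain duration.
- Onset uniform within 2 months of surgery: λ = 6.75 / (6.75 + 2²/12) = 0.953, correlation 0.98.
- Onset anywhere between surgery and entry: covariance 0.5 × 6.75 = 3.375; variance of duration (6.75 + 7.5²)/3 − (7.5/2)² = 6.94; λ = 0.486, correlation 0.49.

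| p1 to p2, r | onset within 2 months: effect, rejection | onset anywhere before entry: effect, rejection |
|---|---|---|
| 60% to 20%, 0.5 | 0.5 × 0.4 × 0.953 = 0.19, 13% | 0.10, 7% |
| 60% to 20%, 1.0 | 0.38, 33% | 0.19, 12% |
| 70% to 10%, 1.0 | 0.57, 64% | 0.29, 21% |

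The rejection rates are simulated with n = 618 and residual SD 1.73. In the mildest case tried (50% to 30%, 0.3 points) the formula gives 0.06 points for early onset, with 7% rejection, and 0.03 for onset anywhere before entry. With onset spread over 0 to 6 months (correlation 0.83), rejection in the three tabulated cases was 10%, 28% and 51%.

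**The case against.** The strongest reply is that confounding has not been shown. The factors in Section B are risk factors for developing chronic pain, whereas every trial patient already has ICBN with DN4 of at least 4. Nothing links age, axillary surgery, prior pain or mood to how long the pain had lasted, and baseline NRS may already absorb part of any effect. This stands, and it limits the point to an estimate that is open to confounding.

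A reader might go further and infer that the estimate is confounded in a known direction. On that reading, patients with short duration are those still on or just off chemotherapy or radiotherapy; they improve when it ends, and the model credits early treatment. The documents do not support this, for three reasons.
- Section B does quote a description of pain starting at or soon after surgery. Under Assessment of Neuropathic Pain, however, it also describes pain appearing weeks or months later. Stratifying at 3 months of duration when entry begins 3 months after surgery also suggests that later onset was expected. Onset within 2 months would put only about 1/9, or 11%, of patients below the cut.
- The statement that pain "which most often improves after discontinuation of treatment" concerns chemotherapy-induced peripheral neuropathy, not ICBN. Nothing comparable is said of radiotherapy.
- The shares and resolution sizes in Illustration 2 are assumed. That adding the factor removes the bias is true by construction.

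A further objection concerns HADS. Baseline mood is measured after the pain period and may be a consequence of longer pain. Adjusting for it could remove part of the effect of interest. This stands and changes the remedy.

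None of this supports the causal wording. The adjustment set is still two variables for a non-randomised exposure.

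**Conclusion.** The point holds in a limited form. The planned duration coefficient is open to confounding by factors the protocol itself names, and reporting it as an impact is not justified. Size and direction cannot be fixed from the documents. Under the assumed inputs, with no true duration effect, the spurious effect over 9 months ranges from near 0 to about 0.6 NRS points. The upper end needs a factor worth a full NRS point that is also strongly related to duration. The effect shrinks with later onset and is nil if the factor is unrelated to duration.

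The matter is minor. It concerns one secondary objective, and the randomised primary comparison is untouched.

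**What to change.** In Section F, extend the pain-duration model as follows.
- Add age, which is already recorded for stratification.
- Add, where the baseline record holds them, breast and axillary surgery type, adjuvant chemotherapy and radiotherapy status at entry, and pre-existing chronic pain.
- Report the duration coefficient before and after this adjustment.
- Add HADS only in a separate, labelled sensitivity model.
- In the objective and the analysis text, replace impact with association, and say that unmeasured confounding remains possible.

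The cost is mainly SAP wording. With about 600 patients the lost degrees of freedom are negligible. The documents do not say whether the surgical, adjuvant-treatment and prior-pain items are collected, so a few baseline fields may be needed, and a rule for incomplete covariates must be stated. If no field can be added, adjusting for age and changing the wording are still possible at almost no cost.

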The screening period extends from 3 months before surgery to 12 months after breast cancer surgery. Patients who agree to participate are scheduled for a screening visit between 3 and 12 months post-surgery. If they present with ICBN, defined by a DN4 score ≥ 4 , they will be included and randomized to receive either pregabalin (standard treatment) or topical capsaicin patch (experimental treatment), both of which are indicated for the management of peripheral neuropathic pain.

Pregabalin will be initiated with a gradual titration to reach a dose of 600 mg/day in two divided doses, depending on patient tolerability.

Capsaicin patches will be applied in a hospital setting to the painful area for 1 hour, with applications scheduled every 90 days.

All patients will undergo assessments at T0 (± 7 days) and T6 (± 7 days) regarding pain evolution (intensity and area), treatment tolerability, and quality of life.

The end of treatment and study follow-up is planned at the final pain-evaluation visit (T6).

F) STATISTICAL CONSIDERATIONS

SAMPLE SIZE DETERMINATION	
Statistical analyses will be performed using R software.
 
A total of 772 patients will be included, allocated into two balanced groups.
 
Sample size calculation
 
An interim analysis is planned once 300 patients have been included (minimum 150 per arm), based on the primary endpoint.
 
Alpha allocation:
 
 - 0.005 for the interim analysis - 0.045 for the final analysis 
Assumptions for calculating the required sample size:
 
 - At baseline, the standard deviation of NRS pain score is estimated at 2.0. - The expected mean difference in NRS (Capsaicin – Pregabalin) is 0. - The non-inferiority margin is set at +0.4 points on the NRS. - One-sided alpha risk: 4.5%. - Statistical power: 80%. 
Under these assumptions, 322 patients per arm are required (644 total). Considering a 20% rate of non-evaluable patients at 6 months, the total required sample size is 772 patients (386 per arm).

----------------------------------	---

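### Month 2 NRS is analysed on complete cases only, with no method valid under missing at random and no sensitivity analysis; the possible bias runs from zero to about half of the 0.4 margin under the assumptions shown

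*Combined protocol and SAP*

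**What the plan says.** Section F, under Handling of missing, unused, or invalid data, sets the rule for the primary outcome scale: "Missing data for the numerical pain scale (NRS), painful area, and PGIC will not be imputed". Two checks on the loss accompany it. The first is a test of how much is missing in each arm: "The proportion of missing data will be compared between arms using a Chi-square test". The second looks at who those patients were at entry, by comparing their baseline characteristics.

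For quantitative variables, section F (planned statistical methods) names Student's t-test or the Wilcoxon test. The one regression concerns pain duration before inclusion. Non-inferiority is tied to the PP population and the follow-on superiority test to mITT. ITT is defined, but no analysis names it. No mixed model, multiple imputation or sensitivity analysis for missing NRS appears.

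The sample size section sets the scale: a margin of 0.4 NRS points, an expected difference of 0 and a baseline SD of 2.0. On loss it says: "Considering a 20% rate of non-evaluable patients at 6 months, the total required sample size is 772 patients (386 per arm". Section C places the primary endpoint at Month 2.

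**The concern.** With a single-visit two-sample test and no imputation, a patient without a Month 2 score contributes nothing. The complete-case difference is then biased whenever the product of the missing fraction and the pain gap (missing minus observed patients) differs between arms.

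Different loss by arm is plausible. The trial is open-label, one arm takes an oral drug titrated according to tolerability and the other receives a patch in hospital. The background section credits capsaicin with a 10% adverse-effect rate and says that systemic analgesics may be poorly tolerated.

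The planned checks do not close the gap. A chi-square test on missing proportions leaves the estimate unchanged, a non-significant result does not show that bias is absent, and the test cannot see equal proportions lost for different reasons. A baseline comparison cannot show how the missing patients' pain developed afterwards. With a margin of 0.4 on a scale with SD 2.0, a bias of one or two tenths of a point matters, and no planned analysis would show whether the conclusion depends on the missing patients.

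**Working it through.** **The plan's own figure.** Inputs from the sample size section: margin 0.4, SD 2.0, true difference 0, one-sided alpha 0.045, power 80%.

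n per arm = 2 × 2.0² × (1.695 + 0.842)² / 0.4² ≈ 322, which matches the plan. The planned 386 per arm is 322 × 1.2 = 386.4. With 20% non-evaluable, 386 × 0.8 ≈ 309 per arm remain, and power without any bias is 78.5%.

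**Bias formula.** Let d be the missing fraction in an arm and g the mean NRS of missing minus observed patients in that arm. The full mean is the observed mean plus d × g. So the bias in the complete-case difference (capsaicin minus pregabalin) is

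bias = dP × gP − dC × gC.

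Higher NRS is worse, so a negative bias favours non-inferiority.

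**Error rates.** SE = 2.0 × √(1/nC + 1/nP), with n = 386 × (1 − d) in each arm. Power at a true difference of 0 is Φ((0.4 − bias)/SE − 1.695). False non-inferiority at a true difference of +0.4 is Φ(−bias/SE − 1.695).

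**One case in full.** Loss is 15% on capsaicin and 25% on pregabalin, with missing patients 1.5 points worse in both arms. Then nC = 328.1, nP = 289.5 and SE = 0.161. Bias = 0.25 × 1.5 − 0.15 × 1.5 = +0.15, and power = Φ(0.25/0.161 − 1.695) ≈ 44%. With the loss reversed, bias = −0.15 and false non-inferiority = Φ(0.15/0.161 − 1.695) ≈ 22%.

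**Range.** The documents give neither d by arm nor g, so every row is an assumption.

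| Missing, capsaicin / pregabalin | Gap, capsaicin / pregabalin | Bias (share of margin) | Main consequence |
|---|---|---|---|
| 20% / 20% | 1 / 1 | 0 | none: power 78.5%, false non-inferiority 4.5% |
| 8% / 12% | 1 / 1 | +0.04 (10%) | power 75%, against 83% without bias |
| 12% / 8% | 1 / 1 | −0.04 (10%) | false non-inferiority 7.6% |
| 5% / 15% | 1 / 1 | +0.10 (25%) | power 61% |
| 15% / 25% | 1 / 1 | +0.10 (25%) | power 57% |
| 25% / 15% | 1 / 1 | −0.10 (25%) | false non-inferiority 14% |
| 15% / 25% | 1.5 / 1.5 | +0.15 (38%) | power 44% |
| 25% / 15% | 1.5 / 1.5 | −0.15 (38%) | false non-inferiority 22% |
| 20% / 20% | 1 / 0 | −0.20 (50%) | false non-inferiority 33% |
| 20% / 20% | 0 / 1 | +0.20 (50%) | power 33% |

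A simulation of 20,000 trials for the 20%/20% case with gaps 1/0 gave a bias of −0.20 and false non-inferiority of 32.6%. In both of the last two rows the expected missing proportions are equal, so the planned chi-square test has nothing to detect.

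**Tipping point.** With an observed difference of 0 and 309 evaluable per arm, SE = 2.0 × √(2/309) = 0.161, and the upper limit is 1.695 × 0.161 = 0.273. That leaves 0.4 − 0.273 = 0.127. With 20% missing on capsaicin, non-inferiority is lost at a shift of 0.127/0.2 ≈ 0.64 points in the imputed capsaicin values (pregabalin unshifted, SE held fixed). A shift of +0.4 moves the estimate by only 0.2 × 0.4 = 0.08, to an upper limit of about 0.353, and cannot overturn this result.

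**The case against.** The strongest reply is that nothing in the documents shows a harmful bias at Month 2. Most of its parts stand as limits on the point:

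- **Time point.** The allowance reads "Considering a 20% rate of non-evaluable patients at 6 months". A reader might infer that 20% of Month 2 scores will be missing. The documents do not say so: the Month 2 rate is not given and may be lower. Non-evaluable is also undefined and, with a PP analysis, could include protocol deviators who do have a score. A lower rate does not remove the issue, as the 5%/15% row shows. (Section F also calls the primary endpoint NRS at T6 in the stopping rules; that is a separate inconsistency.)
- **Tolerability.** A reader might infer that the arms differ greatly. The documents give 10% adverse effects for capsaicin but, for pregabalin, only a 3.5% weight-gain figure and no overall adverse-effect or dropout rate. Plausibly different is as far as they go. Stopping a drug is also not the same as a missing score.
- **Return for the patch.** Reluctance to come back for another application might seem to explain loss in the capsaicin arm. Re-application is at 90 days, after the Month 2 assessment, so it cannot explain missing Month 2 scores.
- **Direction.** A reader might infer that the plan favours capsaicin. The background section points, if anything, to more loss on pregabalin. If those patients have worse pain, the bias runs against capsaicin: in the 1.5-point case false non-inferiority falls to about 0.4% and the harm is lost power.
- **Not imputing is not in itself an error.** A likelihood-based repeated-measures model needs no imputation. But none is planned.

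What survives is that the primary comparison is complete-case and that no planned analysis tests its dependence on the missing patients.

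**Conclusion.** The point holds as a gap in the analysis plan, not as a demonstrated bias. The Month 2 comparison has no method valid under missing at random and no sensitivity analysis, and the planned checks on missingness cannot stand in for either. Over the assumptions shown, the bias runs from 0 to 0.20 points (0 to 50% of the margin). It is zero when missing fractions and pain gaps match across arms. More loss on pregabalin of patients with worse pain costs power. More loss, or worse missing patients, on capsaicin inflates false non-inferiority. The missing fractions by arm and the gaps are assumed, and SD 2.0 is the plan's baseline value applied to the analysed outcome. This is a worthwhile, inexpensive improvement; the documents do not support saying that the trial's conclusion would be wrong.

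**What to change.** For Month 2 NRS, replace the no-imputation rule with one pre-specified method valid under missing at random:

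- a likelihood-based repeated-measures model on T0, T2 and T6; or
- multiple imputation by arm, using baseline NRS, the stratification factors, discontinuation and adverse-event status, and T6 NRS where available.

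Report it in the ITT or mITT population alongside PP. Naming the population matters, because patients excluded from PP stay excluded whatever is imputed.

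Add a delta-adjusted tipping-point table for the capsaicin arm, with shifts running past the point where non-inferiority is lost (about 0.64 points in the example above). A single +0.4 shift is too weak to serve as the only sensitivity analysis. Keep the complete-case analysis as supportive, and keep the planned comparisons of missingness as description. State the loss expected at Month 2 separately from that at 6 months.

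The cost is SAP wording, some programming and possibly slightly wider intervals. The inputs are data that the trial already plans to collect. Because the trial is open-label, the method should be fixed before outcome data are reviewed.
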